6.1.9 Follow-up of Serious, Unexpected and Related Adverse Events

All serious, unexpected and related adverse events, that are unresolved at the time of the patient's termination from the study, will be followed by the site investigators until the events are resolved, subject is lost to follow-up, the adverse event is otherwise explained or has stabilized, or 12 months have passed from the time of last study dose.

7 Assessment of secondary endpoints

1. Re-epithelialization will be graded by trained, masked examiners on days 1, 3, 4, 5, 6, 7, and 8 unless patient re-epithelializes sooner in which case they can skip visits until day 8. Dimensions of the epithelial defects will be directly measured using slit lamp bio-microscopy. The baseline epithelial defect will be measured by surgeons on Day 1 at the time of surgery. Examiners will be masked as to which patients are using pAF vs. placebo. A vertical and horizontal measure of defect in mm will be performed, and defect area calculated. A complete re-epithelialization (absence of a defect) is defined when the measures equal zero.
2. Pain will be measured through a 0-10 scale on days 1, 2, 3, 4, 5, 6, and 7. Participants will rate their peak pain at the end of each day and directly return the forms at their in-person visit on day 8 to the examiners. They will complete a separate survey for each eye.
3. Uncorrected visual acuity will be measured at post-operative day 8, months 1, 3, 6, and 12 by trained physicians.
4. Manifest refraction and best-corrected visual acuity will be measured at months 1, 3, 6, and 12 by trained physicians.
5. Ocular surface staining will be measured at post-operative months 1, 3, 6, and 12 using an area density index.²⁵ This is a published and validated index used to measure corneal staining. Corneal regularity will also be measured at months 1, 3, 6, and 12 with the Surface Regularity Index (SRI) obtained via Zeiss Atlas 9000 Corneal Topography™.

8 Other Medications

- Oral pain medications usage will be tracked for the first 7 days.

9 Patient Withdrawal From Study

- A subject may withdraw their consent at any time without affect to their care.

10 Discontinuation of Study Drug

The study drug will be discontinued if any of the following occur:

- Development of severe ocular infection.
- Any other condition that in the opinion of the treating physician and ophthalmologist are not compatible with participation in this study.

11 Discontinuation of Study

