For the primary efficacy outcome, a mixed effects model with time to healing as outcome and assigned treatment arm as a predictor, including a random effect for each patient to model correlation between eyes in the same participant, will be fit to carry out the primary analysis. A two-sided probability value with an alpha level of 0.05 will be used to test the null hypothesis that time to complete re-epithelialization is not different between the two treatment arms. The primary analysis will be performed on an intention to treat basis.

12.2 Analyses for Other Outcomes:

The key secondary efficacy outcome at 30 days will be analyzed (on a logarithmic scale) using a mixed effects ANOVA model as for the primary aim. Exploratory outcomes will be analyzed in appropriate fashion; for example, each patients pain level (worst in either eye) will be examined on each evaluation day and compared between treatment groups for each day, while each patients peak pain level at any time, and number of days until the patient is pain-free, will be compared

between treatment arms. A Statistical Analysis Plan will fully delineate all analyses to be performed, including additional analyses to assess robustness of the primary and secondary efficacy analyses.

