3.2.2.1 Eligibility for Secondary Analysis

The secondary endpoint is to be evaluated in all PRK-treated eyes among consented and enrolled patients.

3.2.3 *Exploratory Endpoints*

Exploratory endpoints of the pAF after PRK trial, and the populations eligible for each tertiary analysis, include:

- i. Dimensions of epithelial defects as assessed on Days 1 to 8 except Day 2
- ii. Pain as assessed on 0-10 point scale on Days 1 to 7
- iii. Uncorrected visual acuity on Day 8 and at 1, 3, 6, and 12 Months
- iv. Best corrected visual acuity at 1, 3, 6, and 12 Months
- v. Ocular surface staining at 1, 3, 6, and 12 Months
- vi. Corneal Regularity via Surface Regularity Index (SRI) at 1, 3, 6, and 12 months

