10. EFFICACY ANALYSES

10.1 Primary Efficacy Variable Analysis

The analysis of the primary study outcome will include the following test of hypothesis:

H_0 : time to re-epithelialization is not different among eyes receiving treatment with pAF after PRK, compared to eyes receiving placebo drops after pRK.

The alternative hypothesis is:

H_1 : time to re-epithelialization is significantly different among eyes receiving treatment with pAF after PRK, compared to eyes receiving placebo drops after pRK.

For testing the primary hypothesis, a mixed effects linear model with time to re-epithelialization (number of calendar days from PRK to time to complete re-epithelialization) for each eye as outcome, and assigned treatment arm as a predictor will be fit using SAS PROC MIXED. This model will additionally include a random effect for each patient (formally included in the model as each patient’s study ID, defined as a CLASS variable) to model correlation between eyes in the same participant. A two-sided probability value with an alpha level of 0.05 will be used to test the null hypothesis that time to re-epithelialization is not different between the two treatment arms. If the probability value is less than 0.05, regardless of the direction of treatment effect, the null hypothesis above will be considered to be rejected.

The primary analysis will be performed on an intention to treat basis.

All eyes with available outcome data will be included in the model. Any eyes that are not completely re-epithelialized by Day 8 will be assigned a value of 9 days to re-epithelialization in the primary analysis. Any eyes for which time to re-epithelialization is not fully known due to missed visits will be assigned the midpoint of the possible time in the primary analysis (for example, a patient not re-epithelialized in either eye on Day 2, who misses visits on Days 3 and 4 but has complete re-epithelialization in both eyes on Day 5, would be treated as having complete re-epithelialization in both eyes on Day 4 in the primary analysis). Eyes of patients who drop out of the study before Day 8, that do not achieve complete re-epithelialization before dropout, will be treated as missing in the primary analysis, but included in robustness analyses described below.

Results of the analysis above will be accompanied by appropriate presentation (e.g., histograms) of the distribution of number of calendar days to complete re-epithelialization among eyes in each treatment arm.

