10.3 Tertiary Study Outcomes

10.3.1 *Visual Acuity on Other Study Days*

The visual acuity outcome will be evaluated as above for other study timepoints at which acuity is assessed.

10.3.2 *Dimensions of Epithelial Defects*

Epithelial defect areas in each eye will be compared on each study day, graphically and analytically. The approach to assessing differences on each study day will be analogous to that used for the analysis of the primary and secondary study outcomes. We will also fit exploratory linear mixed models, accounting for within-eye correlation across timepoints as well as within-patient correlation between eyes, to model rate of change of defect areas over time.

10.3.3 *Pain Scale on Days 1 to 7*

The analysis of pain diary data will be an important tertiary analysis of this trial. Key quantities of interest include the duration of pain after treatment, and the most severe pain level after treatment. It is expected that some of the pain outcomes described below may show marked skewness; if this is the case, then rank-based analysis (Mann-Whitney Test with associated two-sided 95% Hodges-Lehmann confidence interval for difference between treatment arms) will be used instead of a *t*-test, which will be the preferred approach when appropriate.

Each patient's worst pain level in either eye will be compared for each of the study days that pain scores are evaluated. These distributions will also be shown graphically over time via an approach appropriate for the data distributions such as boxplots. As this is an exploratory outcome, comparisons will be performed and reported separately for each day unadjusted for multiple comparisons.

Using the worse pain level in either eye (assessed on a scale of 0 to 10), the number of days to full resolution of pain (no pain reported in either eye from that day forward) will be calculated, and compared between treatment arms. It is expected that this outcome may show marked skewness; if this is the case, then rank-based analysis (Mann-Whitney Test with associated two-sided 95% Hodges-Lehmann confidence interval for difference between treatment arms) will be used rather than *t*-tests.

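### SAP 10.3.3 gives no value to a patient still in pain on Day 7, so its pain-duration comparison, programmed literally, omits patients because of their outcome, with bias in either direction.

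*SAP*

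**What the plan says.** Protocol section 7 sets the diary window: "Pain will be measured through a 0-10 scale on days 1, 2, 3, 4, 5, 6, and 7". SAP 3.2.3 lists the same window among the exploratory endpoints: "Pain as assessed on 0-10 point scale on Days 1 to 7". Each eye is scored separately, as the day's peak.

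SAP 10.3.3 ranks duration highly: "Key quantities of interest include the duration of pain after treatment". It defines the variable in one clause: "the number of days to full resolution of pain (no pain reported in either eye from that day forward) will be calculated". The worse eye counts, so a score of 1 in one eye is pain. The preferred test is a t-test; if the distribution is markedly skewed, "then rank-based analysis (Mann-Whitney Test with associated two-sided 95% Hodges-Lehmann confidence interval for difference between treatment arms) will be used". Protocol 12.2 has the same comparison in shorter form: "number of days until the patient is pain-free, will be compared". Neither document says what a patient with pain on the last diary day receives.

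For healing, the SAP does deal with outcomes not reached by the last visit. SAP 10.1: "Any eyes that are not completely re-epithelialized by Day 8 will be assigned a value of 9 days to re-epithelialization in the primary analysis". SAP 10.1.1 adds a clustered log-rank analysis in which unhealed eyes are censored at their last evaluation. Both rules are written for re-epithelialization only.

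**The concern.** The variable exists only for patients whose pain has gone by Day 7. Someone who scores 2 on Day 6 and 1 on Day 7 in one eye never reaches a day from which no pain is reported, so the derived dataset holds a blank. A t-test or a Mann-Whitney test then runs on the remaining patients.

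That is selection on the outcome: the patients with the longest pain are the ones without a number, and the two arms may lose different shares. Reducing post-operative pain is a stated secondary objective, and this is the plan's direct measure of how long pain lasts. If the rule is settled only after the data are seen, the choice between omitting, imputing and censoring is also open to influence from the result.

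**Working it through.** **1. Does another rule fill the gap?** SAP 8.2 covers withdrawals and outliers and defers to outcome-specific strategies; for unresolved pain there is none. SAP 10.3.3 even says which day to use when peak pain is tied across days, but gives no rule for pain that has not resolved. The gap is real.

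**2. The plan's own figures.** The only power figures (SAP section 6, Protocol 12.5) concern healing time. They reproduce. For SD 0.5 and ICC 0.5, SE = 0.5 × √(2 × 1.5 / 56) = 0.116, and 0.116 × (1.960 + 0.842) = 0.324 days; the t version with 54 df gives 0.330, against 0.33 stated. They say nothing about pain, so only the 28 completers per arm is carried forward.

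**3. Assumptions.** The documents give no distribution of pain duration, so every pain input below is assumed. Resolution day = time rounded up to a whole day. *Omit* deletes patients with a value above 7; *code 8* gives them a tied worst value. Power is for a two-sided 5% Mann-Whitney test.

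**4. Share unresolved.** For lognormal times, P(T > 7) = 1 − Φ(ln(7/median)/σ).
- Median 4.2, σ 0.35: ln(7/4.2)/0.35 = 1.460, giving 7.2%.
- Median 5.5, σ 0.35: ln(7/5.5)/0.35 = 0.689, giving 24.5%.
- Median 3.6, σ 0.25: ln(7/3.6)/0.25 = 2.660, giving 0.4%.

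**5. One arm slower throughout** (simulated; differences in days, faster arm ahead):

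| Medians, σ | Unresolved, slow v fast | Omit | Code 8 | Full follow-up | Power, omit v code 8 |
|---|---|---|---|---|---|
| 3.6 v 3.1, 0.20–0.25 | under 1% | 0.49–0.51 | about 0.51 | 0.51 | 51–69% either way |
| 4 v 3, 0.4 | 8% v 2% | 0.80 | 1.01 | 1.08 | 61% v 71% |
| 5 v 4, 0.4 | 20% v 8% | 0.57 | 0.88 | 1.09 | 32% v 50% |
| 5.5 v 4.2, 0.35 | 24.5% v 7% | 0.73 | 1.12 | 1.39 | about 50% v 77% |
| 6 v 5, 0.4 | 35% v 20% | 0.41 | 0.70 | 1.08 | 16% v 35% |
| 7 v 6, 0.4 | 50% v 35% | 0.29 | 0.53 | 1.07 | 10% v 26% |

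The 50% in the fourth row varied from 49% to 52% over repeated simulations. The first row borrows the healing means of 3.1 and 3.6 days as medians, purely to show a low end.

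**6. Other patterns.** Here resolvers have medians of 4 (pAF) and 5 (placebo) days with σ 0.3, and unresolved patients are assumed to resolve on Day 10. Differences are pAF minus placebo.

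| Unresolved, pAF v placebo | Omit | Code 8 | Full follow-up | Significant, omit v code 8 |
|---|---|---|---|---|
| 20% v 20% | −0.87 | −0.70 | −0.70 | 63% v 37% |
| 20% v 5% | −0.85 | −0.29 | about 0 (+0.02) | 66% v 14% |

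In the first pattern omission overstates the benefit. In the second it creates one where the full means do not differ. With identical distributions in both arms there was no bias, and 4–5% of trials were significant.

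**The case against.** Three stronger readings are tempting, and the documents support none of them.

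*The SAP excludes these patients.* No sentence says so. Omission is what the definition and tests produce if programmed literally, but an analyst could also assign Day 8 or censor. The SAP's habit elsewhere is to keep extreme outcomes: a value of 9 for unhealed eyes, censoring in the log-rank analysis, and a floor of 20/400 for acuity. That makes omission less certain, but it does not supply the missing rule.

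*The pain effect is understated.* This follows only if patients are omitted and the slower arm also has more of them unresolved. The patterns in step 6 go the other way.

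*The pain analysis is compromised.* Only one derived variable is. Worst pain on each day, Day 7 included, peak pain and its day, and rescue medication use all keep these patients. Persistent pain would show in the Day 7 comparison.

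Two further points stand. The outcome is exploratory: "As this is an exploratory outcome, comparisons will be performed and reported separately for each day unadjusted for multiple comparisons". And part of the shortfall against full follow-up cannot be recovered by any rule, because a seven-day diary does not observe later resolution: code 8 gives 1.12 days against 1.39 in the fourth row. The gain from the fix is therefore the step from *omit* to *code 8*, not to full follow-up.

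**Conclusion.** The concern holds for one variable. Days to full resolution is undefined for a patient with pain on Day 7, the stated tests cannot take a censored value, and the literal result is omission on the basis of outcome. The direction of bias is not fixed. Its size cannot be derived from the documents, because no share unresolved on Day 7 is given. Under the assumed distributions it ranges from nothing of note below 1% unresolved to a loss of about 27 percentage points of power (77% to 50%) at 24.5% against 7%. In the reverse pattern, an apparent benefit reaches significance in 66% of trials.

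This should be changed before unblinding. It does not touch the primary or secondary efficacy test, so it is not critical. It still merits a rule, because the SAP itself gives duration of pain this prominence and a better method needs no extra data.

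**What to change.** In SAP 10.3.3, state that every patient with diary data stays in this comparison, and choose one of two rules:

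- **Worst rank.** A patient reporting pain in either eye on Day 7 is ranked, tied, after all patients whose pain has resolved (recorded as >7, coded 8). The Mann-Whitney test is used for this variable whatever its skewness.
- **Censoring.** Such a patient is censored at Day 7 and the arms are compared by a log-rank test, as already planned for healing. There is one value per patient here, so the clustered version is not needed.

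Under either rule, report the number and proportion unresolved on Day 7 by arm.

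The cost is one or two sentences in the SAP and no new data. The downside is that a mean difference in days gives way to a rank or time-to-event comparison. Under the worst-rank rule, the Hodges-Lehmann interval also depends on the code 8 and should be read with that in mind; the test does not.

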10.3.4 Use of rescue pain medication

Proportions of patients who required use of any pain medication during the first seven days of post-surgical follow-up will be reported and compared between treatment arms by chi-squared approaches. Analogous analyses will be performed for use of narcotics and use of NSAIDs at any time. In addition, the number of days that patients used pain medications will be reported and compared between treatment arms using rank-based tests, again for any type of pain medications as well as for narcotics and NSAIDs alone.

10.3.5 Corneal staining and surface irregularities

Corneal staining density, graded on a scale from 0 to 3, will be reported and compared using rank-based approaches between treatment groups at all evaluation times. To incorporate the effect of correlation between eyes in the same participant, a clustered version of the Wilcoxon test⁴ will be used, using a SAS macro⁵.

Corneal topography will be compared between treatment groups as well. More specifically, surface regularity index (SRI) at each evaluation timepoint will be compared between study arms using mixed models accounting for correlation within eyes in the same participant, using an approach analogous to the analysis of the secondary efficacy outcome of visual acuity above. Baseline SRI will be included in this model as a covariate.

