| Study Product, Dose, Route, Regimen | 
Individual patients will be randomized to one of two post-operative drop regimens, control eyes that will receive placebo saline solution (NaCl 0.9%, Baxter Medical), and study eyes that will receive pAF four times daily for seven days.
 
Both eyes of all patients will otherwise be treated with the standard post-operative drop regimen for our center. This includes moxifloxacin 0.3%, prednisolone acetate 1%, and ketorolac 0.5% on a tapering schedule. A bandage contact lens will also be placed as per standard post-PRK care.
 
All patients will be instructed to use supplemental preservative free artificial tears from individual vials (any brand) no less than 3 but up to 8 times a day for both eyes for the first 7 days.
 |

Continued on next page

Continued from previous page

| | |
|-------------------------|--|
| Statistical Methodology | Standard statistics will be calculated and used to describe the two treatment groups in terms of all study variables. Statistics will be compiled for each variable at the study time points listed in the data collection protocol. |
|-------------------------|--|

2 Objectives

Primary Objectives:

- a. To determine the safety of using pAF to improve ocular surface healing in PRK patients compared to use of placebo drops.

Secondary Objectives:

- a. To determine if pAF hastens re-epithelialization in patients following PRK compared to placebo.
- b. To determine if pAF reduces post-operative pain following PRK compared to placebo.
- c. To determine if pAF affects visual outcome following PRK compared to placebo.
- d. To determine if pAF affects ocular surface staining and corneal regularity following PRK compared to placebo.

3 Rationale and Background

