5.1 Schedule of Events

| | Baseline | Day of Surgery (Friday) | | Days after Surgery | | | | | | | | | | |
|--|----------|----------------------------|---|--------------------|--------|--------|--------|--------|---------------------------------------|----------------------------|----------------------------|-----------------------------|------------------------------|---|
| | | Day 1 (AM) | Day 1 (2 nd visit post- surgery) | Day 3 | Day 4* | Day 5* | Day 6* | Day 7* | Day 8 Friday AM (in-person visit)* | Month 1 (Day 30±10)* | Month 3 (Day 90±14)* | Month 6 (Day 180±30)* | Month 12 (Day 365±30)* | |
| Informed Consent | X | | | | | | | | | | | | | |
| Eligibility | X | | | | | | | | | | | | | |
| Medical History | X | | | | | | | | | | | | | |
| Concomitant medications ² | X | X | X | X | X | X | X | X | X | X | X | X | X | |
| Randomization ³ | | | X | | | | | | | | | | | |
| PRK Surgery | | | X | | | | | | | | | | | |
| Dispense Masked Study Drug ⁴ | | | X | | | | | | | | | | | |
| Study Drug Compliance ⁵ | | | | X | X | X | X | X | | | | | | |
| Pain Assessment ⁶ | | | | X | X | X | X | X | | | | | | |
| Size of Epithelial Defect ⁷ | | | X | | X | X | X | X | X | | | | | |
| Uncorrected VA ⁸ | X | | | | | | | | | X | X | X | X | X |
| Manifest Refraction | X | | | | | | | | | | X | X | X | X |
| Target Post-OP Refraction | X | | | | | | | | | | | | | |
| BCVA ⁸ | X | | | | | | | | | | X | X | X | X |
| Ocular Surface Staining | X | | | | | | | | | | X | X | X | X |
| Corneal Topography | X | | | | | | | | | | X | X | X | X |
| Ocular Adverse Events | | | | X | X | X | X | X | X | | X | X | X | X |

1. The pre-op screening/baseline visit may be performed in 2 separate visits.

2. Record systemic medications at baseline and any subsequent changes; Record start and stop dates of ocular medications prescribed as standard care post-PRK surgery, note any deviations from prescribed regimens.

3. Randomization to study drug assignment will occur when patient presents day of surgery.

4. First dose of study drug applied to each eye at completion of surgery. Three additional doses administered by patient on day of surgery, then 4x per day through Day 7.

5. Patient will document each use of study drug and oral pain medication in diary.

6. Patient will assess highest level of daily pain/discomfort at the end of each day.

7. Grade defect dimensions until healed.

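### The protocol measures staining with an area density index, but SAP 10.3.5 compares density alone and leaves out the collected baseline grade (minor)

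*SAP*

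**What the plan says.** **Measure.** Item 5 of protocol section 7, headed "Assessment of secondary endpoints", states: "Ocular surface staining will be measured at post-operative months 1, 3, 6, and 12 using an area density index". It describes the index as published and validated and cites a grading paper. It does not say how area and density are scored or combined.

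**Analysis.** SAP 10.3.5 says "Corneal staining density, graded on a scale from 0 to 3, will be reported and compared using rank-based approaches between treatment groups", at every evaluation time, and handles the pairing of eyes with "a clustered version of the Wilcoxon test". No part of the SAP mentions a staining area grade or a combined staining index. No baseline staining term is planned. For SRI, the next outcome in that section, the SAP says: "Baseline SRI will be included in this model as a covariate".

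**Baseline data.** The schedule of events (protocol 5.1) has a mark for staining in the baseline column: "Ocular Surface Staining | X".

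**Status.** Protocol section 2 lists as a secondary objective "To determine if pAF affects ocular surface staining and corneal regularity following PRK compared to placebo", and SAP 3.1.2 repeats it. SAP 3.2.3 places "Ocular surface staining at 1, 3, 6, and 12 Months" among the exploratory endpoints, and 10.3 analyses it as a tertiary outcome. Protocol 12.1 lists a between-group comparison of staining without giving it a rank.

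**The concern.** Two kinds of information that the trial plans to collect do not reach the staining analysis.

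The first is area. If the index has an area part and a density part, as its name suggests, a comparison of density alone answers a narrower question than the objective asks. Drops that shrink the stained region while leaving the remaining stain equally dense would show little or nothing. The protocol's claim of validation also belongs to the index, not to one part of it. And while the SAP does not say which staining variable is the main one, the choice among area, density and a combination stays open until the data are seen.

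The second is the baseline grade. Adjusting for a baseline value of the outcome usually sharpens a comparison at almost no cost. The SAP does this for SRI but not for staining, although both serve the same objective, and it gives no reason.

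**Working it through.** **1. The plan's own figure.** The documents give no power or precision figure for staining. The only design table (protocol 12.5, SAP 6) concerns healing time, with 28 patients and 56 eyes per arm. It reproduces: SE = SD × √(2(1 + ICC)/56). For SD 0.7 and ICC 0.75, SE = 0.7 × √(3.5/56) = 0.175. The detectable difference is (1.960 + 0.842) × 0.175 = 0.49 days at 80% power and (1.960 + 1.282) × 0.175 = 0.57 days at 90%, as printed. The table says nothing about staining; it only supplies the sample size used below.

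**2. What a missing area component could cost.** This is an illustration, because the documents do not define the index. Assumptions:
- the index is the sum of area and density, with equal SDs and correlation c from 0.3 to 0.9;
- ICC is 0.5, with 28 patients per arm;
- the total effect is set so that the sum has 80% power.

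With t on 54 df, a single component needs an effect of 0.66 SD for 80% power. The total effect is then 0.66 × √(2(1 + c)) component SDs: 1.06 at c = 0.3 and 1.29 at c = 0.9. The power of density alone depends on how that total is divided:
- equal on both parts (0.53 to 0.64 SD on density): 0.62 to 0.78;
- three quarters on area (0.27 to 0.32 SD on density): 0.20 to 0.28;
- all on area: 0.05, the type I error rate;
- three quarters on density (0.75 × 1.06 = 0.80 SD or more, against the 0.66 needed): above 0.80, so here density alone does better than the sum.

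Density alone is therefore not always the weaker choice. It is weak when the effect is mainly on area.

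**3. What the missing baseline could cost.** Let r be the patient-level correlation between baseline and follow-up staining. It is assumed, because the documents do not give it. In a linear model, covariate adjustment multiplies the residual variance by 1 − r². Testing change from baseline, with equal variances at both times, multiplies it by 2(1 − r). The power column starts from an unadjusted power of 0.80.

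| r | Covariate, 1 − r² | Equivalent sample, 1/(1 − r²) | Power with covariate | Change score, 2(1 − r) |
|---|---|---|---|---|
| 0 | 1.00 | 1.00 | 0.80 | 2.00 |
| 0.3 | 0.91 | 1.10 | 0.835 | 1.40 |
| 0.5 | 0.75 | 1.33 | 0.899 | 1.00 |
| 0.6 | 0.64 | 1.56 | 0.938 | 0.80 |

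Since 2(1 − r) − (1 − r²) = (1 − r)², a change score is never more precise than covariate adjustment. Below r = 0.5 it is worse than no adjustment.

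**4. Check on a 0–3 grade.** The formula in step 3 is linear, while the outcome is a four-level grade compared by ranks. A simulation used 28 patients per arm, two eyes each, and patient mean ranks with and without baseline ranks. Unadjusted power was about 0.76. At latent correlations of 0.3, 0.5 and 0.7, adjusted power was:
- 0.78, 0.82 and 0.92 with well-spread baseline grades (40/30/20/10% at grades 0 to 3);
- 0.77, 0.80 and 0.87 with 80% of baseline eyes at grade 0.

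At latent correlation 0 there was no gain. Type I error was about 0.05 with and without adjustment.

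**The case against.** The best defence has four parts.

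- **The SAP may mean the whole index.** Density could be shorthand for the index. The documents do not define the scoring, so this cannot be excluded, nor can the loss of an area grade be proved. It stands as a reason to clarify the text, because a programmer following the SAP literally would analyse density only.
- **An unadjusted test is legitimate.** Assignment is randomised, and a clustered rank test suits a short ordinal scale in paired eyes. SAP 8.5 leaves the primary analysis free of patient covariates, and the visual acuity model in 10.2 has none, so SRI is the exception. This stands: the omission costs precision and causes no bias.
- **The gain may be near zero.** Severe dry eye, judged by corneal staining, is an exclusion, which may crowd baseline grades near 0. The surgery removes the epithelium, and follow-up staining starts only at month 1. Both could make r low. This stands too.
- **Nothing confirmatory depends on staining.** SAP 8.4 has exploratory outcomes reported as such, without multiplicity control. That limits the importance of the point but does not remove it, because the objective is still named as secondary in both documents.

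A reader might go further and infer that an effect on area would be invisible to the planned test. The documents do not support that: area and density may move together, and an eye whose stained area falls to zero has no density left to grade. A reader might also take the 1.10 to 1.56 sample-size equivalents at r = 0.3 to 0.6 as the gain forgone. They rest on an assumed r and a linear formula, and that range leaves out the possibility of no gain.

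**Conclusion.** The point holds as a minor one. On the text, the protocol names an area density index, the SAP compares density only, and a baseline grade scheduled for collection goes unused while SRI in the same section is adjusted.

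The loss from leaving out area cannot be sized from the documents. Under the stated illustration it runs from none, when the effect is mainly on density, to nearly all power, when it is on area alone. The loss from leaving out baseline is r² of the variance under a linear approximation, with r unknown, and is smaller if most baseline grades are 0.

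It would be wrong to conclude that the staining comparison is biased or that a confirmatory secondary endpoint has been abandoned. The planned test is valid, the SAP ranks staining as exploratory, and the primary efficacy and primary safety analyses are untouched.

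**What to change.** Revise SAP 10.3.5 before unblinding:

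1. Analyse the index the protocol names, area as well as density, scored as in the protocol's cited grading paper, and name one main staining result. If density was meant as the name of that index, say so and give its scoring.
2. Add the baseline staining grade as a covariate, for example in an ordinal mixed model with a random patient effect or in a clustered rank analysis adjusted for baseline ranks. Name the second as the fallback if the first does not fit.
3. Keep the clustered Wilcoxon test as a supportive analysis.
4. Do not use a test on change from baseline, because it loses precision if r is below 0.5.
5. While editing, correct the two citations for the clustered test and its macro. They are numbered 4 and 5, which in SAP 13 are the contact lens study and the power software; the matching entries are 6 and 7.

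The cost is SAP wording and some extra analysis work. The ordinal model may be hard to fit if grades are sparse, hence the named fallback. The protocol already plans the index and the baseline assessment, but the documents do not show the data collection form, so the sponsor should confirm that it records area as well as density.
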